In our ongoing study looking at the relationship between dysmenorrhea, COS and CPP (EH13-094), we planned to determine whether oral contraceptive pills (OCPs), by alleviating menstrual pain could reverse the development of COS. However, our interim analyses of participants in this study identify that many are unwilling to initiate OCPs due to the perceived side effects and fear of hormones. Other interventions to reduce the development of COS also plausibly exist, notably NSAIDs. Therefore, we propose to re-enroll many of the participants from EH13-094 who gave permission for future contact. We will utilize their baseline assessment visit data in order to establish whether naproxen can improve menstrual and bladder outcomes. After consent, prior data will be linked with the current study. We will also open this study to new participants who will be asked to perform a baseline visit (bladder test, pressure tests, EEG, questionnaires and blood draw). Participants will be invited to an open label (non-randomized) prospective trial of naproxen. After six to eight months of diary data, urine monitoring, and blood samples, a repeat visit (bladder test, pressure tests, EEG, questionnaires, and blood draw) will be conducted. The majority of the testing details below have been previously approved for the ongoing study EH13-094.

Additionally, we will investigate whether mechanisms involved in pain sensitivity predict responses to effectiveness of NSAID treatment for menstrual or bladder pain. Several studies identify that women with menstrual pain have central sensory processing abnormalities akin to what is observed in women with chronic pelvic pain states.⁹⁻¹¹ Focused investigation into gynecological risk factors for bladder pain syndrome is of particularly high value, as it more commonly affects women¹², and current treatments, such as pentosan polysulfate,¹³ amitriptyline,¹⁴ or cystoscopic hydrodistension¹⁵ are only modestly effective. The limited efficacy of these treatments reflects the multifactorial mechanisms underlying BPS, particularly in later stages, which may include cross-organ sensitization, central nervous system sensitization, mucosal inflammation, and neuropsychological factors.¹⁶ One underlying hypothesis for this finding is that repetitive episodes of

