dysmenorrhea promote cross-organ or central sensitization. This is supported by clinical observations¹⁷ and experimentally in animal models of provoked uterine inflammation.⁶ Mechanisms involved in central pain modulation can be evaluated with conditioned pain modulation and pressure pain testing^{10,18} and both will be used in this proposal. Additionally, we will look at neural mechanisms using audio and visual tasks¹⁹ with EEG. We will determine whether baseline mechanisms are correlated with menstrual and bladder outcomes. The within subject design also allows us to determine if changes in mechanisms (baseline vs repeat visit) are associated with better outcomes.

Study participants

Inclusion Criteria:

Reproductive-age women (age 18-45) with dysmenorrhea will be recruited. Cases will have: a) average menstrual pain $\geq 5/10$ (0=no pain and 10=the worst imaginable pain) on at least one day during menses or during withdrawal uterine bleeding from cyclic OCs without painkillers, b) menstrual pain in the region between the umbilicus and the perineum, above the level of the inguinal ligament, and c) indication the participant has attempted to resolve pain by medical means (including NSAIDs and/or OCPs). In the circumstance that a participant originally assigned to the dysmenorrhea group does not reach a pain of 5 on any days on the daily diary, this will be handled on a case-by-case basis particularly if they used a continuous around-the-clock, effective pain treatment regimen. Participants who endorse bladder symptoms (subclinical urgency, frequency, bladder pain) on the phone screen or bladder symptoms as reported in EH13-094 will be preferentially recruited (at least 50% of enrolled participants); those who do not endorse bladder symptoms may be determined ineligible. They must not have a formal urological diagnosis such as overactive bladder or painful bladder syndrome.

Exclusion criteria:

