Includes: a) presence of active pelvic or abdominal malignancies (primary or metastatic), b) absence of regular menses (including current pregnancy, recent pregnancy, or active breast feeding), c) active genitourinary infection in the last four weeks, d) unable to read or comprehend the informed consent in English, e) unwilling to complete study procedures, and f) presence of hypertension or risk for developing hypertension, g) unwillingness to take naproxen and/or placebo, h) or contradictions to taking naproxen (allergies, kidney disease, anemia, alcoholism, cardiovascular disease, stomach or intestinal ulcer or abnormal liver function). Participants with a history of epilepsy will not complete the visual unpleasantness task.

Recruitment:

Participants will primarily be recruited based on prior participation in the parent study (EH13-094), which has currently more than 100 potential participants. Additional recruitment may occur from NorthShore's clinical sites in the Chicago-area and from the community through advertising in: NorthShore University HealthSystem's outpatient clinics; web-based advertising; posters and flyers in local businesses (coffee shops, athletic clubs) and on college campuses; referrals

from local gynecologists; and the Illinois Women's Health Registry based at Northwestern University's Feinberg School of Medicine. All flyers and ads will be IRB approved. We will use IRB approved ads from our Recruitment Registry (EH16-117) that informs participants about any of our open studies in our lab. Participants may call our research hotline directly, respond to our online pre-screen, or after they indicate interest and give permission, their doctor will send us their contact information and a research coordinator will call the patient to formally assess eligibility using a phone screen. At the end of the phone screen, participants will be asked if we have permission to put their phone screen and contact information into our recruitment registry (EH16-117).

Phone Screen

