All callers will complete a phone screen to assess eligibility before being scheduled for a screen visit. At the end of the phone screen, all callers will be asked if we have their permission to keep their phone screen information and contact them for future studies. Participants who indicate yes will be added to our recruitment registry (EH16-117) study upon study closeout. Eligible callers will be scheduled for a screen visit. We may attempt to match groups for age and demographics. Thus, in some cases, eligibility on the phone screen may vary based on the study's current need for individuals with certain demographics for each group. We may also require dysmenorrhea participants to endorse bladder symptoms on the phone screen in order for them to be eligible to come in for a screen visit. During the phone screen, we will discuss when their last period occurred and when they anticipate their next period to schedule the study visits. Participants will be instructed not to donate blood before the study visit to avoid excessive blood draw. Participants will receive directions from well-known medical educational web sites (such as <https://www.mayoclinic.org/diseases-conditions/menstrual-cramps/> , <https://www.webmd.com/women/menstrual-cramps>). Our trial is in consensus with expert recommended medical guidelines that are suggested on these web sites.

Study Visits

We will perform 3-4 study visits: a screen visit, a baseline study visit, a blood draw study visit, and a follow-up study visit. Participants that have participated in EH13-094 in the last 12 months will not need to participate in the baseline study visit as the data was collected during the EH13-094 assessment visit.

Consent

Informed consent will be obtained by a trained research assistant at the screen visit before any questionnaires or study procedures are completed.

Questionnaires

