At the screen, baseline and follow-up visit (either in person or over the web using a REDCAP, secure interface) participants will complete the following questionnaires: a) complete medical, surgical, and gynecological history, and b) a psychosocial assessment using short-form PROMIS instruments (pain behavior, pain interference, fatigue, sleep, anxiety, depression, physical function, satisfaction with participation in social roles, and 10 item global health scale).²⁰ Participants will also complete the following pain rating questionnaires (the Interstitial Cystitis Problem and Symptom Indices, the Pain Catastrophizing Scale, Revised Short-form McGill Pain Inventory⁷² and MIDAS headache questionnaire).⁶⁷ These scales have been linked to pain intensity and quality of life

in CPP sufferers, and catastrophizing (rumination, magnification, and feelings of helplessness about pain) is a well-validated intervention target for many cognitive-behavioral approaches for chronic pain.²¹⁻²⁴ Validated, CPP-specific assessment tools will be used to characterize IBS (Rome III criteria)²⁵ and bladder pain symptoms (Genitourinary Pain Index).²⁶ Subjects will also complete the Female Sexual Function Index (FSFI)⁶⁸ and Brief Symptom Inventory (BSI)- based questionnaire containing 6 somatization questions selected from the BSI-18⁶⁹ plus a vision question, and the Complex Medical Symptoms Inventory (CMSI)-General, Fibromyalgia Symptoms, Fatigue, and Vulvodynia sections.^{70,71}

Rapid Bladder Test

At the screen visit, all participants will be asked to undergo a “rapid bladder test.” Participants will be asked to rate their bladder pain on a 0-100 VAS scale when they reach “first urge.” If a participant arrives to the visit already at first urge, we will have them rate their pain and if not ≥ 10 we will wait 15 minutes past first urge and have them rate their pain again. This is because the participant may not have been focusing on the feeling of their bladder. Participants not already at first urge will be encouraged to drink water (at least 20 oz) during the screening visit until they reach first urge at which point a pain rating will be attained. After they reach first urge, they can go to the bathroom and leave their urine sample.

Pelvic Floor Exam:

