Urine: Participants will be told that urine samples will allow us to verify they are taking the study medication as directed. Participants will be asked to freeze urine collected from the evening of day 2 of their menses for each cycle. 6 storage vials will be provided. The urine samples will allow us to verify if participants are taking the provided pills.

Blood: Participants will be instructed to arrive at Evanston Hospital for a scheduled blood draw 1.5-3 hours after ingesting naproxen pills. This will allow us to verify naproxen is sufficiently absorbed to provide therapeutic effects. Only one naproxen absorption blood draw will be performed per participant. Participants will be allowed to choose the most convenient period day for testing, but cannot come on the first day.

Follow up visit:

Six to eight months later, participants will be invited to return for a follow-up visit. Participants will perform the same measurements obtained in the original baseline visit. In the event participants are unable to return for a complete baseline visit, participants will receive a prorated stipend for partial

completion of items (including questionnaires). Participants will bring in any unused study medication to this visit.

Power Analysis/Data Analysis:

The primary outcomes are menstrual pain and bladder pain. Menstrual pain will be evaluated by comparing diary data and questionnaire data from baseline to 6-8 months after treatment. We estimated the needed sample size with a power analysis. Historically, the effects of NSAIDS are known to have a large effect size ($dz > .7$). A power analysis ($\alpha=.05, 1-\beta=.80$) suggests that to detect a more moderate effect of $dz=.7$ sample size of 20 would be needed. To account for a ~20-30% drop out rate, we will recruit 30 participants.

An additional primary outcome is bladder pain as measured by the experimental bladder pain test and the GUPI questionnaire. We estimated the needed sample size with a power analysis. The effects of oral contraceptives on bladder pain had enormous effect size ($dz=2.9$). Unfortunately, too few participants were willing to take oral contraceptives. A power analysis ($\alpha=.05, 1-\beta=.80$) suggests that to detect a more moderate effect of $dz=1$ sample size of 10 would be needed. We will attempt to attain a sample size of $n=20$ to allow detection of and even lower effect size $dz=0.7$ (per the primary outcome for menstrual pain).

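### Choosing re-enrolled women on EH13-094 bladder symptoms while using EH13-094 data as their baseline can build regression to the mean into the bladder primary outcome

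*Combined protocol and SAP*

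**What the plan says.** **Selection.** Inclusion Criteria gives two routes to preference. Women with bladder symptoms "on the phone screen or bladder symptoms as reported in EH13-094 will be preferentially recruited (at least 50% of enrolled participants"). The 50% is a floor, since "those who do not endorse bladder symptoms may be determined ineligible". Phone Screen adds an option: "We may also require dysmenorrhea participants to endorse bladder symptoms on the phone screen".

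**Source.** Recruitment states: "Participants will primarily be recruited based on prior participation in the parent study (EH13-094), which has currently more than 100 potential participants". Power Analysis/Data Analysis plans to recruit 30, so there is room to choose.

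**Baseline.** The background text says of re-enrolled women: "We will utilize their baseline assessment visit data in order to establish whether naproxen can improve menstrual and bladder outcomes". Study Visits limits this to EH13-094 participation within the last 12 months; those women "will not need to participate in the baseline study visit as the data was collected during the EH13-094 assessment visit". The experimental bladder pain test belongs to that visit, so they do not repeat it before naproxen. Other women have a new baseline visit.

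**Outcome.** Power Analysis/Data Analysis: "An additional primary outcome is bladder pain as measured by the experimental bladder pain test and the GUPI questionnaire". Under Questionnaires, the GUPI is in the set completed at several visits: "At the screen, baseline and follow-up visit (either in person or over the web using a REDCAP, secure interface) participants will complete the following questionnaires". The plan does not say which GUPI is the baseline.

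The trial is open label, non-randomized and within-subject. No adjustment for regression to the mean is described.

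**The concern.** Bladder symptoms vary from one occasion to the next. A woman preferred because she reported symptoms at a given time is more likely than average to have been in a bad spell then. If her baseline comes from that time, her later score tends to fall back toward her usual level whether or not naproxen works.

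The plan reads the before-after change as evidence that treating menstrual pain reduces bladder pain. With no control arm, a fall produced by selection looks the same as a drug effect, and it points in the direction of the hypothesis. This is separate from how old the baseline is: it could arise even if the EH13-094 visit was last month.

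**Working it through.** **1. The plan's own figures.** Two-sided paired t-test, alpha 0.05, noncentrality dz·√n. For dz = 1, n = 10 gives power 0.803. For dz = 0.7, n = 19 suffices, and the stated n = 20 gives 0.844. The stated sizes reproduce and are not in dispute. The plan does not state sidedness; one-sided tests would need only 8 and 15.

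**2. Inputs.** From the plan: n = 20, alpha 0.05, at least 50% of women with bladder symptoms. Assumed, because the documents do not give them: correlation ρ of the bladder score between occasions, 0.6–0.8; the more symptomatic half of the pool is selected; the symptom report correlates c₀ with the baseline score (0.6, or 1.0 if selection is on the score itself); no drug effect; normal scores.

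**3. Formulas.** In SD units, the upper half of a normal distribution has mean λ = √(2/π) = 0.798, and λ² = 0.637. Let c₁ be the correlation of the selecting report with the follow-up score.
- Expected fall in a selected woman: m = (c₀ − c₁)·λ. If report and baseline share an occasion, c₁ = c₀·ρ.
- Variance of change: v = 2(1 − ρ) if unselected; vₛ = v − (c₀ − c₁)²·λ² if selected.
- If a share f is selected and exposed and the rest are unselected: mean f·m; variance f·vₛ + (1 − f)·v + f(1 − f)·m².

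**4. One case in full.** Half exposed, c₀ = 0.6, ρ = 0.6. Then c₀ − c₁ = 0.60 − 0.36 = 0.24; m = 0.24 × 0.798 = 0.192; v = 0.8; vₛ = 0.8 − 0.0576 × 0.637 = 0.763. Mean = 0.5 × 0.192 = 0.096. Variance = 0.5 × 0.763 + 0.5 × 0.8 + 0.25 × 0.192² = 0.791, so SD = 0.889. dz = 0.096 / 0.889 = 0.11.

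**5. Results.** Rejection rates are from simulated 20-woman trials; nominal is 5%.

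| Exposed | c₀ | ρ | Mean fall (SD units) | SD of change | dz | Rejection |
|---|---|---|---|---|---|---|
| half | 0.6 | 0.8 | 0.048 | 0.631 | 0.08 | 6% |
| half | 0.6 | 0.6 | 0.096 | 0.889 | 0.11 | 7% |
| all | 0.6 | 0.8 | 0.096 | 0.625 | 0.15 | 10% |
| all | 0.6 | 0.6 | 0.192 | 0.874 | 0.22 | 16% |
| all | 1.0 | 0.8 | 0.160 | 0.612 | 0.26 | 20% |
| all | 1.0 | 0.6 | 0.319 | 0.836 | 0.38 | 36% |

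Most rejections are in the direction of improvement, where the nominal rate is 2.5%.

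**6. Wider inputs.** With ρ 0.5–0.9, the top 25–50% selected, c₀ of 0.5 or 1.0, and half or all exposed, dz runs from 0.04 to 0.70. Only the most extreme corner (ρ = 0.5, top quarter, all women, selection on the score) reaches the planned 0.7.

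**7. Selection on a separate occasion.** If the selecting report correlates equally with baseline and follow-up, c₀ = c₁, the expected fall is 0 and rejection is 5%. This would hold for a phone-screen preference with an EH13-094 baseline if the phone screen correlates equally with both visits. If the selecting report is close in time to the baseline, some regression remains. With c₀ = 0.8, c₁ = 0.6 and ρ = 0.6, the fall is 0.2 × 0.798 = 0.160, the variance 0.8 − 0.04 × 0.637 = 0.775, dz = 0.160 / 0.880 = 0.18, and rejection is about 12%.

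**The case against.** The strongest reply is that the key link is not in the text. The plan does not say at which EH13-094 contact, or on which instrument, symptoms were reported. A reader might infer that one assessment both selected the women and supplied their baseline; the documents allow this but do not state it. That objection stands, and it limits the conclusion to what can happen.

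Three further points reduce the likely size:
- Baseline reuse applies only within 12 months, and new recruits have their own baseline visit. A reader might infer that most of the sample is affected; the share is not given.
- Every caller completes a new phone screen. A woman who endorses symptoms then as well is partly selected for persistent symptoms, which regress less. But requiring endorsement there is optional, so it is not a safeguard.
- The selecting symptoms are urgency, frequency and bladder pain by report, while the experimental test records pain and urgency ratings during filling. The link is probably well below 1.0, which makes the last two table rows a ceiling.

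A reader might also infer that the GUPI is biased in the same way. That is not established: a new GUPI is completed at the screen visit, and the gap is that no baseline is named. The screen visit also includes a rapid bladder test, but this records pain around first urge only. The follow-up visit repeats the baseline-visit measurements, so the rapid test does not replace the missing pre-treatment bladder test.

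None of this removes the mechanism for women who are preferred on EH13-094 symptoms and keep the EH13-094 bladder test as baseline.

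**Conclusion.** The concern holds as a possible bias, clearest for the experimental bladder test. As written, the plan lets EH13-094 symptoms influence selection and lets EH13-094 data be the baseline, with no control arm to reveal the resulting fall.

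The moderate case, with half the women exposed and a report-to-score correlation of 0.6, gives a spurious dz of 0.08–0.11, and rejection rises only from 5% to 6–7%. If every woman is exposed, the figures are 0.15–0.22 and 10–16%. The 20–36% rate should not be read as the expected error rate: it needs every woman to be re-enrolled and selected on the outcome score itself. All these figures rest on assumed correlations and selection intensity. Even the 0.38 ceiling under the main assumptions is well below the planned dz of 0.7. The bias would therefore exaggerate a bladder effect, or occasionally create a significant one; it is unlikely to account for an effect of the planned size. The remedy is cheap enough to adopt despite that uncertainty.

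**What to change.** - **Inclusion Criteria:** strike the route that gives preference for symptoms reported in EH13-094, so that the bladder preference rests only on the phone screen that all callers complete.
- **Power Analysis/Data Analysis:** flag any women already chosen on EH13-094 symptoms. Report the bladder change with and without them, and separately by baseline source (EH13-094 or new visit).
- **GUPI baseline:** name one rule that applies to all women. If the screen-visit GUPI is chosen, including for women already selected on EH13-094 symptoms, state that some regression may remain where phone-screen selection came shortly before it (step 7 of the working).

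Cost: a one-line eligibility amendment, a sentence defining the baseline and slightly more analysis work, with no new procedure. A few women with past but not current bladder symptoms lose priority.

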Many of the women experience severe menstrual pain, yet undermanage their pain level by not taking a sufficient amount of NSAIDs. Notably, biochemical analyses demonstrate that the administration of naproxen prior to the initiation of the COX-2 cascade results in nearly complete suppression of prostaglandin synthesis; attempting to block synthesis afterwards only leads to a gradual and incomplete suppression.¹ The single, but underpowered trial, comparing menstrual pain relief between prophylactic versus response use to pain with ibuprofen did not find a difference.² It is possible that differences in prophylactic use of naproxen and ibuprofen could be due to different preferential binding to COX-1 and COX-2 receptors. Aside from this trial, clinical investigators have not sufficiently investigated prophylactic use of NSAIDs prior to the onset of menses. Although an educational trial regarding prophylaxis did demonstrate increased patient knowledge, reduction of menstrual pain was not evaluated.³ Therefore, in the present study we will establish whether prophylactic and adequate dosages of Naproxen are capable of reducing menstrual pain more than response use. Secondly, we will establish whether reduction of menstrual pain with optimized naproxen use can reduce bladder pain via cross-organ sensitization or central sensitization. We hypothesize that cross-organ sensitization (COS) is the mechanism by which dysmenorrhea may lead to some forms of chronic pelvic pain. Uterine inflammation during menstruation likely contributes to chronic pelvic pain (CPP) by triggering neurogenic inflammation in adjacent organs.⁴ This COS has been demonstrated with experimental injury and infection in animal models.^{5,6} Our prior findings discussed above^{7,8} motivate our present central hypothesis: *dysmenorrhea produces CPP via repetitive COS episodes.*

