The baseline and follow-up visit includes internal vaginal pressure-pain threshold testing, which is similar in nature to the pelvic floor portion of a gynecological exam. Thus, for participants who have never had a gynecological exam, a study nurse or study doctor may complete a simple exam of the pelvic floor at the screen to promote understanding of the internal vaginal pressure-pain threshold testing that will be completed at the baseline and follow-up visit. This ensures that the integrity of our data is not biased by unfamiliar experience. Participants will be asked whether they have ever had a gynecological exam on the phone screen and a simple exam of the pelvic floor for those that say they have never had an exam will be scheduled into their screen.

Creatinine Test:

A creatinine test will be conducted to check for kidney function for all participants. This will be done via blood draw at the screen visit.

Menstrual Diaries:

All participants will be asked to complete daily diaries for a full menstrual cycle to assess their baseline scores.

[figure not shown]
Baseline Visit:

A baseline visit will be performed for all participants that have not conducted an assessment visit for EH13-094 in the last 12 months: **[Note all of these assessments are the same as the assessments approved in EH13-094]**. The baseline visit will be scheduled to occur during the luteal phase (15 to 25 days after the start of the prior menstrual cycle). Participants will be asked to confirm that menstrual pain or bleeding has not started during the baseline visit.

Food: Baseline Visits are very long so we will offer snacks to the participants (e.g., teddy grahams and fruit roll-ups).

Instrumentation: During the baseline visit, EMG and EKG electrodes, and respiratory rate monitors will be applied and information will be recorded throughout the visit. EMG leads will be placed on the lower abdomen during the bladder testing to measure muscular recruitment. The abdominal EMG leads will be moved to the knees once the bladder pain test is completed. The EKG leads and respiratory belt are placed to measure autonomic activity. The autonomic activity will be recorded to verify nociceptive experience. During each testing session, participants will also have their blood pressure and pulse taken.

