Participants will be instructed on usage of prophylactic and recommended dosage of naproxen. Participants will be instructed to take one Naproxen (500 mg) pill in the morning and one again 12 hours later the first day before their anticipated first day of menses. The research coordinators will help interpret the menstrual pain calendars for the participants to predict their next menstrual cycle. Participants will continue to take a pill twice daily for the first 3 days of their menstrual period. If participants still have menstrual pain the following day, they will be instructed to continue taking 2 pills a day until their pain stops. Any unrelieved pain can be treated with acetaminophen (according to directions listed on the package). Participants will continue taking pills before and during their period for 6-8 months until the follow up visit is performed. In the event that a participant has been taking Naproxen for 3 consecutive days and has been asymptomatic (i.e., not started their menses) we will have them stop taking the study medication. The research staff will instruct them to start taking it again as soon as they start their period.

The dosage does not exceed the maximal daily recommended over the counter dose for Naproxen (1500 mg first day, 1000 mg subsequent days).

Between visit measurements:

Diaries: On each day of menstrual bleeding and/or pain, participants will complete a daily diary. The daily diary will be completed using REDCap and asks them to rate their menstrual, bladder, and bowel pain (using a numeric rating scale where 0-no pain, 10-worst pain imaginable), describe any bleeding, and what time the study medication was taken. They will be asked to record any other pain reliever/medication they tried that day (heat pads, muscle relaxers, herbal teas, etc) in the notes section. They will be instructed to not take any additional painkillers except acetaminophen during their menses or while taking the study medication. Outside of their menses, they can treat their pain however they normally would (flu, headache). To protect confidentiality, subjects will not enter identifying information and only use their assigned subject ID #.

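### Menstrual-cramp web directions are placed at the phone screen, ahead of the baseline diary cycle that is the only comparator, so the measured change could shrink by an unknown amount

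*Combined protocol and SAP*

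**What the plan says.** The Phone Screen section of the combined protocol and SAP comes first in the participant's path: "All callers will complete a phone screen to assess eligibility before being scheduled for a screen visit". In the same section, participants are given material on menstrual cramps: "Participants will receive directions from well-known medical educational web sites". Two menstrual-cramp web addresses follow, and then the statement "Our trial is in consensus with expert recommended medical guidelines that are suggested on these web sites".

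The baseline diary is described further on, under Menstrual Diaries, in one sentence: "All participants will be asked to complete daily diaries for a full menstrual cycle to assess their baseline scores". That sentence neither limits analgesics nor lists the items recorded.

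The intervention comes later still, under Naproxen: "Participants will be instructed on usage of prophylactic and recommended dosage of naproxen". The painkiller restriction and the log of other remedies appear after that, in the Diaries paragraph of Between visit measurements: "They will be instructed to not take any additional painkillers except acetaminophen during their menses or while taking the study medication".

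The opening section gives the aim, which is to establish whether "prophylactic and adequate dosages of Naproxen are capable of reducing menstrual pain more than response use". The design is one open-label, non-randomized group. Power Analysis/Data Analysis compares menstrual diary and questionnaire data at baseline with those at 6-8 months.

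**The concern.** With no concurrent control, the baseline cycle stands in for the control condition, which by the stated aim is response use. The intervention is largely instruction in how to take an NSAID, together with supplied naproxen. The protocol's own premise is that many women take too little. Advice on menstrual cramps that the trial says it agrees with is therefore a plausible, if weaker, form of the same instruction. As the sections are ordered, it reaches women before the comparator is measured.

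If some women act on the advice, their baseline pain is already lower, the change from baseline is smaller, and the amount varies between women. A small observed change could then mean either that the study regimen adds little or that the baseline had moved toward it.

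**Working it through.** **Order of steps.** Phone screen with web directions, then screen visit and consent, then baseline diary cycle and baseline visit, then naproxen instruction and treatment diaries, then follow-up at 6-8 months. The timing of the directions is read from their placement under Phone Screen. No sentence delays them until after baseline.

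**Inputs from Power Analysis/Data Analysis.** dz=.7, alpha=.05 (sidedness not stated), power .80, n=20, 30 recruited, dropout about 20-30%.

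**The plan's own figure.** For a two-sided paired t-test with the exact noncentral t (df = n-1, noncentrality = dz·√n):

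- dz=.7 needs n=19 (power 82%). At n=20 power is 84%, so the stated 20 reproduces.
- Completers expected from 30 recruited: 30 × 0.7 = 21 to 30 × 0.8 = 24. Power is 86% at 21 and 91% at 24.
- The smallest dz with 80% power at n=20 is 0.66. The reserve is (0.70 - 0.66)/0.70, or about 6% of the planned effect.

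**Sensitivity (assumed values).** Suppose a fraction q of women already have a share k of the effect in their baseline cycle. In units of the SD of the paired differences, each of those women loses .7k. The mean change becomes .7(1-qk) and the variance becomes 1 + q(1-q)(.7k)², so

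dz* = .7(1-qk) / √[1 + q(1-q)(.7k)²]

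- q=.25, k=.25: .7 × .9375 / √(1 + .1875 × .175²) = .656/1.003 = 0.65
- q=.25, k=.5: .7 × .875 / √(1 + .1875 × .35²) = .6125/1.011 = 0.61

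| Case | dz | Power, n=20 | Power, n=24 |
|---|---|---|---|
| No shift | 0.70 | 84% | 91% |
| q=.25, k=.25 | 0.65 | 79% | 87% |
| q=.25, k=.5 | 0.61 | 73% | 81% |

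More extreme inputs give larger losses. With q=.5 and k=.5, dz is 0.52 and power is 59% at n=20 and 68% at n=24. Nothing in the documents suggests that reading web pages would have an effect of that size. The documents supply neither q nor k.

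**Who is exposed.** For new participants, all baseline measurements follow the phone screen. Women with an EH13-094 assessment visit in the last 12 months reuse those visit data, which predate this contact. For them, only the new diary cycle and any screen-visit questionnaires can be affected.

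**The case against.** The strongest reply is that self-treatment at baseline is what the trial means to compare against. Response use means taking analgesics once pain starts, so a baseline cycle without an analgesic ban suits the question. This stands. A reader might infer that the missing painkiller limit is itself a defect, or that eligibility based on pain without painkillers contradicts the baseline diary. Given the stated aim, the documents support neither. Only a shift in self-treatment caused by the directions is at issue.

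Second, the content of the directions is not given. The statement of consensus says that the trial agrees with the sites. It does not say that women are told at the phone screen to follow the study regimen. This also stands, and it limits the point to what could happen.

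Third, a reader might infer that the site could not know who self-treated at baseline. That is too strong. The inclusion criteria allow case-by-case handling when diary pain stays below 5, "particularly if they used a continuous around-the-clock, effective pain treatment regimen", which presupposes some knowledge of analgesic use. The one diary form that is described does log other pain relievers, and nothing says the baseline diary is a different form. The fair statement is that recording and handling at baseline are not specified.

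Fourth, participants must already have tried medical treatment, the pages are public, and women will probably learn of the naproxen plan at consent. The added effect of the directions may be small, and moving them will not remove all anticipation. This bears on size. It does not justify giving aligned advice just before the comparator is measured.

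**Conclusion.** The point holds as a weakness in the order of steps. The directions are placed ahead of the only comparator for the menstrual primary, and if they change NSAID use they move that comparator toward the intervention. Any such bias is toward no effect. It could mask a benefit or make a small change hard to interpret, but it would not create a false positive.

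Its size is unknown. The illustrative falls in power (84% to 79% or 73% at n=20; 91% to 87% or 81% at n=24) rest on assumed shares. They would apply equally to any baseline NSAID benefit that the planned dz does not already allow for, and they do not estimate what the directions add. A reader might conclude that the baseline already contains the intervention or that the trial is underpowered. The documents show neither: the stated sample size reproduces, and the expected 21-24 completers give some margin. The conclusion depends on reading the timing from the section placement.

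**What to change.** 1. Give the web-site directions at the naproxen instruction step, after the baseline diary cycle and baseline visit, and state in the protocol what they contain and when they are given. This is the main change.
2. State that the baseline diary carries the same medication items as the treatment diary: which pain relievers were taken, when, and what other remedies were used.
3. Describe the menstrual contrast as study naproxen versus usual self-treatment, and report baseline NSAID use descriptively. With about 20 completers, a split by baseline NSAID use could not support separate inference.

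What women may take at baseline does not change.

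The cost is a protocol edit and, if the baseline form differs from the treatment form, a REDCap edit. Women would see publicly available pages about one cycle later, and the baseline diary may be slightly longer.
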